8.4.7 Dose-limiting Toxicity

The DLTs and MTD are defined using the NCI CTCAE version 4.03.

Dose-limiting toxicities will be drug-related toxicities (considered related or possibly related to) and graded using NCI CTCAE version 4.03 occurring during the DLT period and include:

- Non-hematologic toxicity \geq grade 3 (except diarrhea, nausea, and vomiting unless lasting >3 days despite optimal supportive care)
- Confirmed (with a second measurement after 24 hours) non-hematologic appropriately graded laboratory findings of grade ≥ 3 that were \leq grade 1 at baseline
- Hematologic toxicity:

- Grade 4 neutropenia ≥ 5 days, or grade 3 neutropenia with fever (fever is $> 38.4^{\circ}\text{C}$)
- Grade 4 thrombocytopenia, or grade 3 thrombocytopenia lasting > 7 days or with bleeding
- Any other toxicity assessed as related to RGT100-PEI, and which, in the opinion of the study Investigator(s) and the Sponsor physician constitutes a DLT

The DLT period will be 4 weeks. Evaluation of the available safety data over this DLT period will be required from at least 3 subjects per DL and per Group (A or B) before a decision is made whether to enroll additional subjects at the same, or the next DL.

Note: Subjects withdrawn from the study before the completion of the DLT period for reasons other than DLT will be replaced.

During dose escalation, escalation to the next DL will occur only if the safety and tolerability (including DLTs) data are acceptable as determined during the dose escalation meetings by the SRC. If any change is made to the grade or causality of an AE during the study that may alter its DLT status, the Sponsor and SRC must be informed immediately as this may affect dose escalation decisions.

The following toxicities will not be considered as DLTs:

- Grade 3 AE of tumor flare (defined as local pain, irritation, or rash localized at sites of known or suspected tumor)
- Grade 3 irAE that resolves to grade ≤ 1 within 7 days.

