9 TIMING OF STUDY PROCEDURES

Participants will undergo a screening period of up to 3 weeks. The study treatment period will be approximately 4 weeks (shorter if the subject withdraws, and longer if there are delays to dosing due to toxicities). All subjects will be followed up for 30 days following their final dose of RGT100-PEI or until resolution or stabilization of all treatment-related AEs, whichever is later. If no progressive disease (PD) is seen after a 30-day follow-up period, subjects will be in follow-up for another 30 days (total of 60 days after last injection), which defines the end of the trial. Further survival follow-up will be performed every 3 months for a period of 24 months outside of the main study.

Subjects will provide written informed consent before any study-related procedures are performed. The timing of study assessments is provided in Table 3 for Group A and Table 4 for Group B.

Table 3: Group A (Cutaneous) Schedule of Assessments

Trial Visits, Investigations, and Interventions	Screening	Treatment Period								End-of- Treatment Visit	Follow-up Visit		
	Day -21 to Day -1	Week 1		Week 2		Week 3		Week 4		Week 5	Week 9	Week 13 ^a	
		Day 1 Inj 1	Day 4 Inj 2	Day 8 Inj 3	Day 11 Inj 4	Day 15 Inj 5	Day 18 Inj 6	Day 22 Inj 7	Day 25 Inj 8	Day 29 (±3 days)	30 days after last injection (±7 days)	60 days after last injection (±7 days)	
RGT100-PEI injection ^a		+	+	+	+	+	+	+	+				
Informed Consent	+												
Medical History	+												
Eligibility Criteria	+												
Pregnancy Test ^b	+									+			
ECG	+									+	+	+	
Physical Examination ^c	+	+		+		+		+		+	+	+	
ECOG Performance Status	+	+		+		+		+		+	+	+	
Vital Signs ^d	+	10+	10+	5+	5+	5+	5+	5+	5+	+	+	+	
Overnight observation		+	As deemed appropriate by the investigator										
Height/Weight	+												
Hematology ^e	+	++	+	++	+	++		++		+	+	+	
Clinical Chemistry ^e	+	++	+	++	+	++		++		+	+	+	
Urinalysis ^e	+	++	+	++	+	++		++		+	+	+	
Autoimmunity ^f	+					+				+	+		
Infectious Diseases ^g	+									+	+		
Immunoglobulins ^h	+					+				+	+		
Immuno-monitoring ⁱ	+	+++							+++	+	+	+	
PK (RGT100-PEI) ^j		7+							7+				
Mutation Status ^k	+												
Tumor Assessment and Photography ^l	+	+		+		+		+		+	+	+	

Trial Visits, Investigations, and Interventions	Screening	Treatment Period								End-of- Treatment Visit	Follow-up Visit	
	Day -21 to Day -1	Week 1		Week 2		Week 3		Week 4		Week 5	Week 9	Week 13 ^a

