10.4 Safety Variables

10.4.1 Adverse Events

10.4.1.1 Adverse Event Definition

An AE is defined as any untoward medical occurrence in a clinical study subject administered a medicinal product which does not necessarily have a causal relationship with this treatment. An AE can therefore be any unfavorable and unintended sign (including an abnormal laboratory finding), symptom, or disease temporally associated with the use of a medicinal (investigational) product, whether or not it is related to the medicinal (investigational) product. This includes an exacerbation of pre-existing conditions or events, intercurrent illnesses, drug interaction or the significant worsening of the indication under investigation that is not recorded elsewhere in the eCRF under specific efficacy assessments. Anticipated fluctuations of pre-existing conditions, including the disease under study that do not represent a clinically significant exacerbation or worsening need not be considered AEs.

The Investigator will monitor each subject for clinical and laboratory evidence of AEs on a routine basis throughout the study. Should an Investigator become aware of any study drug-related SAEs following this period these must also be reported as stated in [Section 10.4.4.3](#). Adverse event monitoring starts from the time the subject consents to the study until they complete the trial. All reportable AEs will be followed to a satisfactory conclusion. Any reportable drug-related AEs that are unresolved at the follow-up visit are to be followed up by the Investigator until resolution or stabilization.

AEs will be elicited by asking the subject a non-leading question, for example, “Have you experienced any new or changed symptoms since we last asked/since your last visit?” AEs should be reported on the appropriate page of the eCRF.

Each separate AE episode must be recorded. For example, if an AE resolves completely or resolves to baseline and then recurs or worsens again, this must be recorded as a separate AE. For AEs to be considered intermittent, the events must be of similar nature and severity.

Tumor progression is not an AE. However, the medical conditions associated with disease progression must be documented as AE.

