10.4.1.7 Follow-up of Adverse Events

Adverse events should be followed to determine the outcome.

AEs that are serious or considered related or possibly related to study drug or study procedure must be followed up until the event is resolved, resolved with sequelae or until, in the opinion of the Investigator, the event is stabilized, has been fully assessed and does not require further follow-up or determined to be chronic. Details of AE resolution must be documented in the eCRF.

For all SAEs, where important or relevant information is missing, active follow-up should be undertaken.

All other AEs must be followed up by the Investigator until the AE is resolved, resolved with sequelae or the end of the period of observation (= last study visit), whichever comes first.

Subjects should be followed up for 30 days (or 60 days for subject who have not progressed at Day 30) after receiving the last dose of study drug, and any AEs that occur during this time should be reported according to the procedures outlined above. If AEs that are serious and considered related or possibly related to study drug or study procedure are ongoing at the time of subject's last study visit, all attempts should be made to receive the final outcome.

A follow-up report must be completed when an SAE resolves, is unlikely to change, or when additional information becomes available. In case the SAE is a suspected unexpected serious adverse reaction (SUSAR) follow-up information must be provided within the timelines as requested by the INC Research Safety & Pharmacovigilance.

If new or amended information on a reported SAE becomes available, the Investigator can report this on a new SAE form using the completion guidelines. If using the original form to notify further information, all new or amended information need to be initialed and dated in order all changes are clearly identified.

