11.1.8 Handling of Missing Data

Missing data will not be replaced. Analyses will be performed considering all data observed for the respective analysis sets. For missing AEs and concomitant medication start and end dates the followings rules will be applied:

Partial/missing start date:

- Missing day: Impute the first of the month unless month is same as month of first dose of study drug then impute first dose date
- Missing day and month: impute 1st January unless year is the same as first dose date then impute first dose date
- Completely missing: impute first dose date unless the end date suggests it could have started before this in which case impute the 1st January of the same year as the end date.

Partial/missing end date:

- Missing day: Impute the last day of the month unless month is same as month of last dose of study drug then impute last dose date
- Missing day and month: impute 31st December unless year is the same as last dose date then impute last dose date

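### Section 11.1.8 moves some partial AE and medication end dates back to the last dose date, so events recorded after treatment can end before they start (minor data-handling error)

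*Combined protocol and SAP*

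**What the plan says.** Section 11.1.8 introduces its date rules with "For missing AEs and concomitant medication start and end dates the followings rules will be applied". For end dates there are two:

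- Day missing: "Impute the last day of the month unless month is same as month of last dose of study drug then impute last dose date".
- Day and month missing: "impute 31st December unless year is the same as last dose date then impute last dose date".

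Neither rule requires the imputed end to fall on or after the start. Neither is limited by death, last contact or data cut-off. No other section overrides them.

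The same document plans to record data after the last dose. Section 9 states that "The study treatment period will be approximately 4 weeks", and Tables 3 and 4 put the last scheduled injection at Day 25 (Group A) or Day 22 (Group B). Section 10.4.1.7 then says "Subjects should be followed up for 30 days (or 60 days for subject who have not progressed at Day 30) after receiving the last dose", with AEs in that time to be reported. Section 10.4.1.1 adds: "Any reportable drug-related AEs that are unresolved at the follow-up visit are to be followed up by the Investigator until resolution or stabilization". For medications, section 8.4.11 runs to the end-of-treatment visit. Tables 3 and 4 continue collection at Weeks 9 and 13, restricted after Week 9 to further anti-cancer medication.

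**The concern.** The end-date rules mirror the start-date rules. For a start date, falling back on the first dose date keeps an uncertain event inside the treatment period, which is the cautious direction. For an end date, falling back on the last dose date assumes that the event stopped when treatment stopped. An event that began after the last dose cannot have done so, and one still active at that dose did not.

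The result is impossible date pairs in the AE and medication listings, wrong values for any duration derived from them, and wrong answers on whether a medication overlapped an event. A toxicity that leads to stopping treatment is a natural candidate, because it usually resolves after the last dose.

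**Working it through.** The plan states no figure on this point, so there is nothing to reproduce. The check applies the two rules as written to calendar dates.

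**Worked cases.** Assume first dose on 2 March and last dose on Day 25, which is 26 March. The events are ordinary low-grade AEs. Duration = end − start + 1.

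| True event | Known part of end date | Imputed end | True duration | Imputed duration |
|---|---|---|---|---|
| 28–31 March | month | 26 March | 4 | −1 (end 2 days before onset) |
| 24–31 March | month | 26 March | 8 | 3 |
| 10–20 April | year only | 26 March | 11 | −14 (end 15 days before onset) |
| 10–20 April | month | 30 April | 11 | 21 |
| 5–8 March | month | 26 March | 4 | 22 |

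The first three rows show the fault. The fourth shows that an end in a later known month is not shortened. The fifth shows that an event which truly ended before the last dose is lengthened.

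**How often, among events with a partial end date.** Assumptions that are not in the documents: last doses spread evenly over the 365 days of a non-leap year (seven months of 31 days, four of 30, one of 28), AEs of 5 days counted inclusively, and onset spread evenly over the 30 or 60 days after last dose. In a month of L days, the number of last-dose dates for which a day k days later is still in that month is max(L − k, 0).

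1. *Day missing, end before start.* Onset d = 1 to 30 days after last dose gives an end k = d + 4 = 5 to 34 days after it. The count per month is (L − 5)(L − 4)/2: 351, 325 and 276 for L = 31, 30 and 28. The total is 7 × 351 + 4 × 325 + 276 = 4,033. Divided by 365 × 30 = 10,950, this is **36.8%**. Over 60 days the numerator is unchanged, because no longer lag stays in the month: 4,033 / 21,900 = **18.4%**.
2. *Only the year known, end before start.* The share of last-dose dates with the end in the same year is 1 − k/365. Over 30 days the mean k is 19.5, giving 1 − 19.5/365 = **94.7%**. Over 60 days k runs from 5 to 64, mean 34.5, giving 1 − 34.5/365 = **90.5%**.
3. *Any event truly ending 1 to 30 days after last dose, end moved earlier.* With the day missing, the count per month is L(L − 1)/2: 465, 435 and 378. The total is 7 × 465 + 4 × 435 + 378 = 5,373, and 5,373 / 10,950 = **49.1%**. The mean move is the sum of k(L − k) divided by this count, (7 × 4,960 + 4 × 4,495 + 3,654) / 5,373 = 56,354 / 5,373 = **10.5 days**, with a maximum of 30. With only the year known, the share is 1 − 15.5/365 = **95.8%**.

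Only the calendar relative to the last dose matters, so Groups A and B give the same percentages.

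**The alternative.** Imputing the last day of the known month with no last-dose exception gave no reversed and no shortened event over all 365 first-dose dates, for onsets from 24 days before to 60 days after last dose and durations of 1, 5 and 15 days. It does lengthen events: 5–8 March becomes 5–31 March, which is 27 days against 22 under the present rule and 4 in truth.

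**The case against.** **Consequences are limited.** Section 11.1.6 plans AE incidence, grade, seriousness and relationship, together with listings. None of the planned counts uses an end date, and no AE-duration or medication-duration summary is specified. A medication begun after the last dose is still recognisable from its start date. This stands, and it is why the point is minor.

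**DLT status.** A reader might infer that the rule can turn a DLT into a non-DLT, because section 8.4.7 has duration-based criteria, among them the exemption "Grade 3 irAE that resolves to grade" 1 or below within 7 days. The documents do not support that:

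- DLTs are judged during the study on Safety Review Committee review (8.4.7, 10.5), and nothing says that imputed dates enter it.
- Section 10.4.1.3 records an AE of changing severity once, at its highest grade, so its end date is not the date of the fall to grade 1.
- The criterion of more than 7 days concerns thrombocytopenia, which can be dated from the scheduled blood counts.
- An illustration in which a grade 3 event stays above grade 1 while a further injection is given conflicts with the interruption rule in section 8.4.9.4.

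**Partial dates may be rare.** Section 10.4.1.2 requires an end date for every resolved AE, and section 12.4 has missing data queried. Both reduce the number of partial dates. Section 11.1.8 exists for those that remain, so the rule still needs to be right.

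**The rule is not one-sided.** It lengthens events that ended before the last dose in the same month or year, and the replacement lengthens events too. This stands. The difference is that the replacement never reverses dates and does not shorten events.

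**Detail is deferred.** Sections 11.1 and 11.1.5 point to a separate, more detailed SAP, which could replace the rule. Nothing in the documents reviewed shows that it does.

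**Conclusion.** The rule is wrong as written, and the error is minor. That it can reverse or cut dates follows from the text alone and needs no assumption beyond the planned post-treatment collection.

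The percentages do rest on the assumptions shown. They are conditional on a post-treatment AE having a partial end date, and the documents give no frequency for that. The 60-day figures also treat collection as even to Day 60, whereas the 60-day visit is for non-progressors only and after Week 9 only new, possibly related AEs are captured.

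A reader might also take 49.1% and 95.8% as the share of AEs with reversed dates, since the same arithmetic gives the share of onsets within 30 days that fall in the month or year of last dose. Reversal requires the event's end to fall in that month or year as well, which is why the 5-day figures are lower. None of these is a share of all AEs.

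Nor does the rule truncate every AE ongoing at the last dose. It acts only where the end date is partial and its known month or year matches. An AE that is still ongoing carries no end date (10.4.1.2) and is untouched.

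**What to change.** In section 11.1.8, or in the SAP with the change recorded as section 11.1.1 requires:

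- Delete the last-dose-date exception from both end-date rules.
- Impute the last day of the known month, or 31 December if only the year is known.
- Cap the result at the earlier of death and last study contact, and never set it before the start date.
- State that imputed dates are not used to determine DLT status.

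In the example above, the 28–31 March and 24–31 March events would then carry their true end date. If last contact were 60 days after the last dose (25 May), the year-only April event would end on 25 May, lasting 46 days against a true 11. That is too long, but possible.

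The cost is a few sentences and a small change in programming, with no effect on sites. The downside is that some events are lengthened, which the cap limits. No new query process is needed, because sections 10.4.1.2 and 12.4 already cover chasing missing dates.

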11.2 Determination of Sample Size

11.2.1 Dose Escalation Phase

Between 9 and 24 evaluable subjects will be recruited to each group (Group A and Group B) in the dose escalation phase of the trial in a 3 + 3 design to establish a RP2D as explained in earlier sections of the protocol. Each dose escalation needs to be agreed to by the SRC based on the definitions in this protocol.

11.2.2 Expansion Phase

Up to 60 evaluable subjects will be recruited to the expansion phase of the trial at the RP2D to further delineate safety and clinical activity of RGT100-PEI. There will be up to 4 groups of 15 subjects each with selected tumor indications. No formal power calculations were performed to obtain the suggested sample size. During further therapy, subjects will continue to be assessed for safety and tolerance, as well as for preliminary evidence of anti-tumor efficacy of RGT100-PEI.

Hence the number of subjects has been based on the desire to obtain adequate safety, tolerability, anti-tumor activity, PK, data while exposing as few subjects as possible to the investigational product and procedures.

11.3 Protocol Deviations

Subject safety is the primary concern of the Investigator, and this protocol recognizes that in some instances, not all protocol-specified details may be followed exactly. If it is deemed that the Investigator is acting urgently in the subject's best interest (e.g., in an emergency) at a given time, investigations or procedures may be omitted or conducted outside the specified timeframes. In the event of the need to significantly deviate from the protocol for any deviations that could potentially impact the subject's safety or the efficacy of study drug, the Investigator should contact the CRO or Sponsor as soon as possible to permit a decision as to whether or not the subject is to continue in the study, if possible. These deviations will be reported to the ethics committee in line with the sites ethics reporting requirements

The nature and reasons for any protocol deviation will be recorded in the subject's eCRF. Additional investigations obtained outside the protocol will not be considered a protocol deviation, as these may be required by the subject's usual treating doctors (e.g., a chest X-ray or urine test in the evaluation of an infection by the subject's local doctor), or in the event that the subject requires attendance at an emergency department for reasons unrelated to the study.

12 QUALITY ASSURANCE AND QUALITY CONTROL

12.1 Audit and Inspection

All aspects of the study conduct may be subject to internal or external quality assurance audit to ensure compliance with the protocol, GCP requirements, and other applicable regulation or standards. It may also be subject to a regulatory inspection. Such audits or inspections may occur at any time during or after the completion of the study. Investigators and their host institution(s) should understand that it is necessary to allow auditors/inspectors direct access to all relevant documents, study facilities and to allocate their time and the time of their staff to facilitate the audit or inspection visit. Anyone receiving notification of a regulatory inspection that will (or is likely to) involve this trial must inform the CRO without delay.

12.2 Risk Assessment

A risk assessment and a monitoring plan will be prepared before the study opens and will be reviewed throughout the study if necessary in the light of significant changes while the study is ongoing or in response to outcomes from monitoring activities. Monitoring plans will be amended as appropriate.

12.3 Monitoring

Regular monitoring will be performed according to the monitoring plan. Data will be evaluated for compliance with the protocol, completeness and accuracy. The Investigator and institutions involved in the study will permit study-related monitoring and provide direct on-site access to all study records and facilities if required. They will provide adequate time and space for the completion of monitoring activities.

Study sites will also be monitored centrally by checking incoming data for compliance with the protocol, consistency, completeness and timing. The case report data will be validated using appropriate set criteria, range and verification checks. The study site must resolve all data queries in a timely manner. All queries relating to key outcome and safety data and any requiring further clarification will be referred back to the study site for resolution. For other non-critical data items, CRO staff may resolve data queries centrally providing the correct answer is clear. Such changes will be clearly identified in the eCRF and the study site informed.

Study sites will also be monitored remotely and/or by site visit as necessary to ensure their proper conduct of the trial. CRO staff will be in regular contact with site personnel to check on progress and deal with any queries that they may have. The Investigator is expected to action any points highlighted through monitoring and must ensure that corrective and preventative measures are put into place as necessary to achieve satisfactory compliance.

